6.9. Performance Status

The performance status, depending on age, will be measured using the Karnofsky performance status score for subjects ≥ 16 years or Lansky performance status score for subjects < 16 years (Appendix E and Appendix F, respectively) at screening, on Day 1 of every cycle and at the Treatment Discontinuation Visit.

6.10. Echocardiography

An echocardiography will be performed at screening, at the end of Cycles 4 and 12 and at the Treatment Discontinuation Visit. If clinically indicated, echocardiography may be repeated during the study at the discretion of the Investigator.

6.11. Electrocardiogram

An electrocardiogram will be done at screening and at any unscheduled visits (only if clinically indicated).

6.12. Height and Weight

Height will be collected only at screening and on Cycle 1 Day 1. However, weight will be collected at screening and Day 1 of every cycle for dose adjustment if weight changes by 10% or more during the Treatment Phase.

6.13. Chest X-ray

A chest X-ray is not needed if a previous chest X-ray taken within 4 weeks prior to Day 1 of Cycle 1 is available and not clinically significant, otherwise a chest X-ray will be performed at screening.

6.14. Laboratory Assessments

Laboratory testing will be performed locally at the study sites. It is the responsibility of the Investigator to assess the clinical significance of all abnormal values as defined by the reference ranges from the laboratory. Requirements for reporting laboratory abnormalities as AEs can be found in Section 11.3. Laboratory parameters outside the normal range, which are judged by the Investigator to be clinically significant (eg, those which require concomitant therapy or procedures, changes in study treatment or further diagnostic measures) will be recorded as AEs in the CRF. This does not hold true if the laboratory abnormality in the view of the Investigator is caused by the underlying disease. Clinically significant laboratory abnormalities at screening may result in a subject being ineligible for the study and should not be captured as an AE. Any abnormal values that persist should be followed at the discretion of the Investigator. The

Investigator should file all copies of the local laboratory reports including faxes with the subject's medical chart.

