6.14.2. Chemistry Laboratory Assessments

Serum chemistries including sodium, potassium, chloride, bicarbonate, calcium, phosphorus, blood urea nitrogen (BUN), creatinine, glucose, albumin, total protein, alkaline phosphatase, total bilirubin, direct bilirubin, aspartate aminotransferase (AST), alanine aminotransferase (ALT), and lactate dehydrogenase (LDH), and uric acid will be evaluated by the local laboratory at screening, on Days 1, 2, 4, 8, 15, and 22 of Cycle 1, on Days 1, 8, 15, and 22 of Cycle 2, on Day 1 of every cycle thereafter, at the Treatment Discontinuation Visit, on the 28-day Follow-up Visit, and at unscheduled visits (if clinically indicated). Serum chemistry laboratory values will not be collected on a laboratory CRF; instead, laboratory abnormalities that are considered AEs should be reported on the AE CRF (see Section 11).

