11. ADVERSE EVENTS

11.1. Monitoring, Recording and Reporting of Adverse Events

An AE is any noxious, unintended, or untoward medical occurrence that may appear or worsen in a subject during the course of a study. It may be a new intercurrent illness, a worsening concomitant illness, an injury, or any concomitant impairment of the subject's health, including laboratory test values (as specified by the criteria below), regardless of etiology. Any worsening (ie, any clinically significant adverse change in the frequency or intensity of a pre-existing condition) should be considered an AE. A diagnosis or syndrome should be recorded on the AE page of the CRF rather than the individual signs or symptoms of the diagnosis or syndrome.

Abuse, withdrawal, sensitivity or toxicity to an investigational product should be reported as an AE. An overdose, accidental or intentional, whether or not it is associated with an AE should be reported on the overdose CRF. For the definition of overdose see Section 8.2.2. Any sequelae of an accidental or intentional overdose of an investigational product should be reported as an AE on the AE CRF. If the sequelae of an overdose is an SAE, then the sequelae must be reported on an SAE report form and on the AE CRF. The overdose resulting in the SAE should be identified as the cause of the event on the SAE report form and CRF but should not be reported as an SAE itself.

In the event of overdose or exaggerated response, the subject should be monitored as appropriate and should receive supportive measures as necessary. There is no known specific antidote for a lenalidomide overdose. Actual treatment should depend on the severity of the clinical situation and the judgment and experience of the treating physician.

All subjects will be monitored for AEs during the study. Assessments may include monitoring of any or all of the following parameters: the subject's clinical symptoms, laboratory, pathological, radiological or surgical findings, physical examination findings, or other appropriate tests and procedures.

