11.3. Abnormal Laboratory Values

An abnormal laboratory value is considered to be an AE if the abnormality:

- results in discontinuation from the study;
- requires treatment, modification/interruption of IP dose, or any other therapeutic intervention; or

- is judged to be of significant clinical importance, eg, one that indicates a new disease process and/or organ toxicity, or is an exacerbation or worsening of an existing condition.

Regardless of severity grade, only laboratory abnormalities that fulfill a seriousness criterion need to be documented as an SAE.

If a laboratory abnormality is one component of a diagnosis or syndrome, then only the diagnosis or syndrome should be recorded on the AE page/screen of the CRF. If possible, the laboratory abnormality should be recorded as a medical term and not simply as an abnormal laboratory result (eg, record thrombocytopenia rather than decreased platelets).

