11.1.3. Adverse Events of Special Interest

Selected TEAEs/ serious AEs (SAEs) of interest, including second malignancies and cardiovascular events, as determined by the mechanism of action, known class effects, or TEAEs observed to date will be summarized. Standardized MedDRA queries (SMQs) will be used in the search strategy for some of the selected AEs of special interest related to study drug, intending to aid in case identification. The groupings of selected AEs, described by one phrase or topic term will be determined by clinicians based on SMQ or relevant search terms and provided to statistician, prior to database lock.

Analysis of AEs of special interest will be presented with tabulations for: summary of TEAEs of interest by category, TEAEs of interest, NCI-CTCAE grade 3 or 4 TEAEs of interest, TEAEs of interest related to study medication, NCI-CTCAE grade 3 or 4 TEAEs of interest related to study medication, serious TEAEs of interest, serious TEAEs of interest related to study medication, serious TEAEs of interest and TEAEs of interest leading to study medication discontinuation, TEAEs of interest by CTCAE maximum grade 1 or 2 and 3 or 4 and TEAEs of interest by CTCAE maximum grade. The following AE of interest categories and preferred terms include but are not limited to:

- Thrombocytopenia and bleeding
- Neutropenia and infection
- Venous thromboembolism
- Cutaneous reactions
- Hypersensitivity and angioedema
- Diarrhoea and constipation
- Peripheral neuropathy
- Cardiac failure and cardiac arrhythmia
- Renal failure
- Ischaemic heart disease (previously myocardial infarction)
- Interstitial lung disease (interstitial pneumonitis)
- Liver function laboratory abnormalities
- Second primary malignancies (SPMs)

- Tumor lysis syndrome (TLS)
- Tumor flare reaction (TFR)
- Graft versus host disease (GVHD)

Frequency distributions for shift from baseline to the maximum CTCAE grade during treatment period will be presented for all grades and focusing on grade 3 or 4.

All AEs of special Interest will be identified by appropriate MedDRA preferred term.

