11.4.2. Chemistry Laboratory Assessments

Serum chemistries including sodium, potassium, chloride, bicarbonate, calcium, phosphorus, blood urea nitrogen (BUN), creatinine, glucose, albumin, total protein, alkaline phosphatase, total bilirubin, direct bilirubin, aspartate aminotransferase (AST), alanine aminotransferase (ALT), and lactate dehydrogenase (LDH), and uric acid will be evaluated by the local laboratory at screening, on Days 1, 2, 4, 8, 15, and 22 of Cycle 1, on Days 1, 8, 15, and 22 of Cycle 2, on Day 1 of every cycle thereafter, at the Treatment Discontinuation Visit, on the 28-day Follow-up Visit, and at unscheduled visits. Serum chemistry laboratory values will not be collected on a laboratory eCRF; instead, laboratory abnormalities that are considered AEs should be reported on the AE eCRF page. No descriptive analysis of the chemistry laboratory results will thus be provided.

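### Protocol 6.14 exempts laboratory abnormalities attributed to leukemia from AE recording, against 11.1 and 11.3, and for chemistry no other analysed data would show what was left out

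*Protocol*

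**What the plan says.** **When a laboratory abnormality is an AE.** Protocol 11.1 defines an AE broadly, "including laboratory test values (as specified by the criteria below), regardless of etiology". The criteria are in 11.3. Besides causing discontinuation from the study, an abnormality qualifies if it "requires treatment, modification/interruption of IP dose, or any other therapeutic intervention". A further route rests on the investigator's judgement, and there an abnormality counts when it "is judged to be of significant clinical importance, eg, one that indicates a new disease process and/or organ toxicity". No exception is made for the disease under study.

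Protocol 6.14 first refers the reader there: "Requirements for reporting laboratory abnormalities as AEs can be found in Section 11.3". It then gives its own rule. Abnormalities the investigator judges clinically significant, including those that lead to a change in study treatment, are recorded as AEs. The next sentence takes some of them out: "This does not hold true if the laboratory abnormality in the view of the Investigator is caused by the underlying disease".

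**What reaches the database.** Protocol 6.14.2 states: "Serum chemistry laboratory values will not be collected on a laboratory CRF". Only abnormalities considered AEs are entered, on the AE page. SAP 11.4.2 follows: "No descriptive analysis of the chemistry laboratory results will thus be provided". For hematology, by contrast, Protocol 6.14.1 records WBC, ANC, absolute blasts and platelets. SAP Table 6 gives reference ranges for WBC, ANC and platelets only.

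**What is to be reported.** SAP 11.1.3 lists "Liver function laboratory abnormalities", renal failure and tumor lysis syndrome (TLS) among the events of special interest. Protocol 10.7.4 plans baseline-to-worst grade shifts for laboratory results it does not name.

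**The concern.** Two sites can see the same abnormal value, judge it alike, and handle it differently. One following 6.14 leaves it out when leukemia is thought to be the cause; one following 11.1 and 11.3 records it and marks it as not suspected. In relapsed or refractory AML the disease will often be a plausible explanation, and a single-arm study has no comparator against which to check the attribution.

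For blood counts, the values in the CRF give some check on what was omitted. For chemistry there is none in the analysis data. At stake is whether the reported frequency of liver and renal laboratory abnormalities, which fall within named safety topics, reflects what happened or partly reflects each investigator's opinion about cause. The primary endpoint and the stage decisions are not affected.

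**Working it through.** The plan states no figure for this point, so the check is mainly a comparison of text.

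**1. Which abnormalities are AEs?**

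| Case | Under 11.1 and 11.3 | Under 6.14 |
|---|---|---|
| Clinically significant, attributed to lenalidomide or of unclear cause | AE | AE |
| Clinically significant, attributed to leukemia | AE, attribution in the causality field | Not an AE |
| Leads to a change in study treatment, attributed to leukemia | AE | Not an AE |
| Diagnosis or syndrome such as TLS or renal failure | AE, recorded as the diagnosis | Outside the sentence, which concerns laboratory abnormalities |

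The second and third rows conflict. An example is the renal hold in Protocol 8.2.1, which applies to a confirmed creatinine clearance below 70 mL/min whatever the cause. If the investigator attributes the fall to leukemia, the interruption makes it an AE under 11.3 but not under 6.14. The study drug record would show the interruption and its reason, but not the creatinine value or its grade.

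**2. Can the analysis data show what was left out?** For chemistry, no. Values are not in the CRF and are not analysed, so entry on the AE page is the only route into the report.

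**3. Direction and size.** If the true rate of such abnormalities is p and a share f is omitted because it is attributed to leukemia, the reported rate is p × (1 − f). This cannot exceed p, so the exception can only lower the count. Neither p nor f is in the documents. The following is an illustration, assuming p from 5% to 30%, f from 0% to 75%, and the planned 43 evaluable subjects. Expected reported number = 43 × p × (1 − f). The probability of seeing at least one, in brackets, is 1 − [1 − p(1 − f)]^43.

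| p | f = 0% | f = 25% | f = 50% | f = 75% |
|---|---|---|---|---|
| 5% | 2.2 (0.890) | 1.6 (0.807) | 1.1 (0.663) | 0.5 (0.418) |
| 10% | 4.3 (0.989) | 3.2 (0.965) | 2.2 (0.890) | 1.1 (0.663) |
| 20% | 8.6 (1.000) | 6.5 (0.999) | 4.3 (0.989) | 2.2 (0.890) |
| 30% | 12.9 (1.000) | 9.7 (1.000) | 6.5 (0.999) | 3.2 (0.965) |

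At f = 0 nothing is lost. The table shows how strongly the result depends on an unknown share; it is not an estimate.

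**4. Data already generated.** From the chemistry schedule in 6.14.2, panels through Cycle 4 are: screening 1, Cycle 1 six, Cycle 2 four, Cycles 3 and 4 one each, treatment discontinuation 1, 28-day visit 1. The total is 1 + 6 + 4 + 1 + 1 + 1 + 1 = 15. Four analytes in the maximum of 47 subjects give 4 × 15 × 47 = 2,820 values. This is an upper bound, since not every child will complete four cycles.

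**The case against.** The strongest reply is that 6.14 itself names 11.3 as the place for the reporting requirements, and 6.14.2 sends sites to Section 11. A site that follows those pointers loses nothing. This stands as a reason not to call the counts biased. It does not remove the conflict, because the exception follows the pointer in the same section and nothing ranks one above the other.

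Several stronger readings are tempting, and the documents do not support them:

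- *That chemistry results are lost.* Local reports are filed in the medical chart (6.14), and abnormalities considered AEs go on the AE page. What is missing is a laboratory CRF record and an analysis.
- *That TLS, renal failure and hepatic failure escape reporting.* The sentence covers laboratory abnormalities. Diagnoses and syndromes are recorded as such under 11.1 and 11.3, and TLS and renal failure are separate special-interest categories.
- *That the DMC cannot see whether the dose rules in 8.2.1 were triggered.* Reductions and interruptions are recorded and summarised by reason (SAP 9.7). The general interruption rules also apply only to toxicity at least possibly attributed to lenalidomide, which is hard to fit within an exception for disease-caused abnormalities. The renal hold lacks that wording.
- *That the pharmacokinetic analysis is compromised.* Entry requires creatinine clearance or GFR above 70 mL/min/1.73 m², the SAP summarises PK by age class, and SAP Section 16 drops the population PK analysis.

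Two further points stand. Protocol 10.7.4 promises shifts only for selected results, so no commitment is broken; limiting chemistry capture is a design choice. And deleting the 6.14 sentence outright would go too far. It covers hematology as well, and 8.2.1 treats myelosuppression as universal in this disease, so every disease-related cytopenia needing transfusion would become reportable under 11.3.

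**Conclusion.** The conflict between Protocol 6.14 and Protocol 11.1 and 11.3 is real in the current text and unresolved. For isolated ALT, AST, bilirubin and creatinine abnormalities, the AE page is the only analysed source, and following 6.14 can only reduce the number entered there.

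The size of the reduction is unknown. It depends on which section sites follow and on how often they attribute an abnormality to leukemia, and the documents give neither. A reader might infer that hepatic and renal toxicity is under-counted. What is shown is a possible loss in one direction that the analysis data could not reveal, not an established undercount.

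The change is worth making: it concerns the completeness of safety data on named topics, and the measurements already exist.

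**What to change.** 1. **Protocol 6.14, 11.1 and 11.3.** Reconcile the wording so that the underlying-disease exception does not apply to chemistry abnormalities, and record attribution in the causality assessment that 11.2.3 already requires for every AE. The exception may stay for disease-related cytopenias, whose key counts are already collected, provided 11.1 and 11.3 are worded to match.
2. **Protocol 6.14.2.** Record creatinine, total bilirubin, ALT and AST in the CRF from the panels already scheduled.
3. **SAP 11.4.2.** Add baseline-to-worst CTCAE grade shift tables for these four analytes, using the protocol's fixed upper limits for AST (50 U/L) and ALT (45 U/L). Creatinine and bilirubin would need reference limits added to SAP Section 18.5.

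The cost is data entry, at most about 2,820 values through Cycle 4, and the added tables. No extra blood is drawn and no dosing rule is touched. More laboratory AEs will be listed as not suspected. The four analytes do not include the electrolytes and uric acid relevant to TLS; isolated abnormalities of those would be covered by the reconciled AE rule but not by recorded values. The amendment that put ANC and platelets in the CRF is not a precedent, since its stated reason was that they form part of the response assessment.

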6.14.1. Hematology Laboratory Assessments

Hematology testing including red blood cell (RBC) count, hemoglobin, hematocrit, mean corpuscular volume (MCV), WBC count and manual differential count (including blasts %, immature myeloid, absolute monocyte count, absolute neutrophil count [ANC]), and platelet count will be evaluated by the local laboratory at screening, on Days 1, 8, 15, and 22 of Cycles 1 and 2, on Day 1 of every cycle thereafter, at the Treatment Discontinuation Visit, on the 28-day Follow-up Visit, and at unscheduled visits (if clinically indicated). White blood cell count, absolute neutrophil count, absolute blast count, and platelet count will be recorded in the CRF, all other hematology laboratory values will not be collected on a laboratory CRF; instead, laboratory abnormalities that are considered AEs should be reported as AEs on the AE CRF (see Section 11). Whenever a hematology sample is collected for a complete blood count (CBC), a peripheral blood smear will be used to assess a manual blood count differential.

6.14.2. Chemistry Laboratory Assessments

Serum chemistries including sodium, potassium, chloride, bicarbonate, calcium, phosphorus, blood urea nitrogen (BUN), creatinine, glucose, albumin, total protein, alkaline phosphatase, total bilirubin, direct bilirubin, aspartate aminotransferase (AST), alanine aminotransferase (ALT), and lactate dehydrogenase (LDH), and uric acid will be evaluated by the local laboratory at screening, on Days 1, 2, 4, 8, 15, and 22 of Cycle 1, on Days 1, 8, 15, and 22 of Cycle 2, on Day 1 of every cycle thereafter, at the Treatment Discontinuation Visit, on the 28-day Follow-up Visit, and at unscheduled visits (if clinically indicated). Serum chemistry laboratory values will not be collected on a laboratory CRF; instead, laboratory abnormalities that are considered AEs should be reported on the AE CRF (see Section 11).

6.14.3. Urinalysis (dipstick)

Urinalysis will include at a minimum specific gravity, pH, glucose, protein, ketones, blood, leukocyte esterase and nitrites, and will be performed at screening and at unscheduled visits (if clinically indicated). A microscopic examination (including casts, RBCs, and WBCs) should be performed in the event of a positive result for (at a minimum): blood, leukocyte esterase, or nitrites.

6.15. Concomitant Medications/Procedures

All subjects will have concomitant medications and procedures recorded from the time of signing the ICF/IAF until the 28-day Follow-up Visit. A complete list of all medications (prescription, over the counter, nutritional, fiber supplements, etc.), dose, dosing regimen, and start and stop dates used prior to and during the study will be recorded on the CRF. Refer to Section 9 for a listing of permitted and prohibited concomitant medications.

6.16. IP Administration

Investigational product administration will be accurately recorded including, but not limited to, date of administration, dose and any changes in dosage administration (eg, interruption or reduction in dosing due to an AE).

Females of child bearing potential (FCBP) should not handle or administer lenalidomide unless they are wearing gloves. All subjects should not extensively handle the lenalidomide capsules or oral suspension. The lenalidomide capsules should not be broken, chewed, or opened and should be maintained in the packaging until ingestion. Refer to the subject diary and the manual on preparation, administration, and handling of the lenalidomide oral suspension for specific details.

In investigational studies, lenalidomide will be dispensed through a qualified healthcare professional (including but not limited to, nurses, pharmacists and physicians). These healthcare professionals will be trained by Celgene in requirements specific to counseling of subjects. Once trained, these healthcare staff will counsel subjects prior to lenalidomide being dispensed to ensure that the subject has complied with all requirements (including use of birth control and pregnancy testing for FCBP) and that the subject understands the risks associated with lenalidomide. This step will be documented with a completed Education and Counseling Guidance Document and no lenalidomide will be dispensed until this step occurs. Counseling includes verification with the subject that required pregnancy testing was performed and results were negative.

A Lenalidomide Information Sheet will be supplied each time lenalidomide is dispensed.

6.17. IP Dispensing

Lenalidomide should be dispensed on Day 1 of every cycle including the OEP. Only enough lenalidomide for 1 cycle of therapy will be dispensed with each cycle of therapy. The first dose of lenalidomide will be administered at the study center after the completion of all clinical procedures required for Cycle 1 Day 1 with the exception of the collection of PK sampling. When multiple capsules are required to make up the accurate daily dosage, detailed instructions will be provided to the subject to ensure accurate dosages are taken ([Appendix B](#)).

Refer to [Appendix C](#) for dosing guidelines for the lenalidomide oral suspension.

Detailed instructions on preparation, administration, and handling of the lenalidomide oral suspension will be provided in a separate manual.

